2.3.6 Electromagnetic navigation for liver biopsies

Electromagnetic (EM) tracking for registration of preoperative images during procedures maps conventional US and CT images for “fusion guidance” [7-19]. Over almost the past 2 decades, the NIH navigation system has integrated electromagnetic tracking of needles and US probes with custom software to allow registration and fusion with three-dimensional images to improve target visualization during needle-based procedures (Figure 9 and Figure 10).

We have used anthropomorphic multimodality injectable interventional phantoms such as Model 57 (CIRS, Norfolk, VA) for a qualitative feasibility studies of EM tracking to demonstrate this application in different clinical scenarios using different imaging modalities to locate the lesion.

For instance, in a feasibility study over a decade ago, using EM tracking alone to navigate to a simulated hot PET lesion using ¹⁸F containing fiducials, PET/MR data set was acquired and the PET scan DICOM images were used to navigate a tracked needle to the internal target. DICOM images were transferred to navigation software and a tracked 22-gauge needle (with a sensor coil embedded in the tip) was placed toward the internal target with electromagnetic tracking guidance. MR scan verification was performed.

Abbreviated Title: ICG for Hepatic Biopsies

Version Date: 09/09/2025

PET and MR datasets were also successfully loaded and registered to the phantom for navigation within metabolic and functional datasets. An internal radiopharmaceutical target was located with electromagnetic tracking with a tracked needle (Figure 11). This technique has been used successfully as a part of an NIH clinical trial for 15 years, and has also been commercialized or duplicated by at least 20 companies.

[figure not shown]

Figure 10. Electromagnetic tracking system components and setup: **(a)** electromagnetic tracking system set up and rationale. **(b)** Components of image-guided system incorporating electromagnetic tracking for abdominal interventions.

A swine model was used to evaluate the feasibility of EM tracking alone. Our studies showed that prospective use of the EM navigation system allows needle and electrode placement with higher confidence in all cases and provides valuable target information that is unavailable by conventional image guidance in most cases. For instance in one of our decade-old studies, the tracking technology enabled 22 needle and electrode placements in 19 procedures; these 22 placements would have had a high risk of technical failure with conventional image guidance only, owing to lack of target localization [11]. These were primarily cases in which the target lesions were visible only on an arterial phase CT scan or on prior PET or PET/CT scan and were then brought into the procedure by image registration with the navigation CT (Figure 11).

The technology was especially enabling for liver targets that were visible only during brief arterial phase enhancement on contrast-enhanced CT scan. The additional information allowed completion of biopsies in less time than they would have taken with conventional guidance, based on the number of failed needle positioning attempts with CT guidance only.

[figure not shown]

Figure 11. Use of pre-procedural PET and MR for needle navigation in a phantom. **(A)** T2-weighted MR image of phantom with gadolinium fiducials (arrows). **(B)** CT/PET image of interventional phantom with 6 mCi of 18F fiducials (arrows) could also be used for needle navigation. **(C)** Tracked needle position (small arrow) is displayed near internal target (large arrow) from pre-procedural PET during tracked needle insertion.

[figure not shown]

Figure 12. Navigation display at the NIH Clinical Center (A-C). Display showing the virtual needle aligned with the target identified on arterial phase-enhanced computed tomography scan. (D) Fiducial markers were placed the patient's skin to facilitate registration process. E) Non-contrast-enhanced confirmation scan of needle position does not show the target lesion. F) After rigid registration of the confirmation scan (pseudocolored) with the arterial contrast-enhanced scan (gray-scale background) in the vicinity of the target lesion, the correct alignment of the needle with the target is confirmed.

Additionally, fusion guidance significantly improves angle recent study, the addition of needle and US tracking improved needle path off-target error from $17.8 \text{ mm} \pm 17.1$ to $3.3 \text{ mm} \pm 3.1$ and changed the insertion angle by $13.3 \text{ degrees} \pm 6.5$. We showed that registration and use of pre-procedural diagnostic or metabolic images enabled identification and localization of targets and had a direct impact on outcomes in interventions [11].

2.3.7 Combination EM and OMI System

The combined integrated platform provided simultaneous optical and EM feedback during simulated ex vivo and real in vivo animal biopsy. EM was used to place the needle roughly near the ICG target, and the optical signal was used to fine-tune and verify precise tip location at the optical source in phantoms and in live Woodchucks with liver tumors (data on file). The ICG signal was predictive of tumor presence on histology biopsy samples using a combined system.

Abbreviated Title: ICG for Hepatic Biopsies

Version Date: 09/09/2025

[figure not shown]

Figure 13. Color means ICG present = tumor

[figure not shown]

Figure 14. White light Optical POC box ICG imaging

2.3.8 Handheld OMI

The OMI is a handheld endoscopic instrument consisting of an FDA-cleared and clinically used pediatric cystoscope-urethroscope (Model 27033 AA; Karl Storz, Tuttlingen, Germany) illuminated by a safelight cable attached to an 808 nm laser excitation source (Stryker IRF L10 Light Source and Safelight Cable) with an adjustable user feature in the Endoscopic Near-Infrared visualization (ENV) mode that can pass coaxially through the introducer of a standard 17-gauge core biopsy system (see **Figure 6**).

The eyepiece of the pediatric cystoscope-urethroscope is attached to high-definition endoscopic camera system sensitive to the visible and infrared spectrums. The optical image is transferred from the surgical site to the camera unit which is attached to the camera head (Mako; Allied Vision Technologies) and the light output is by a filtered band-pass filter that is compatible with the laser excitation source.

The imaging pediatric cystoscope-urethroscope tip is the only component that is in direct contact with the subject and will be sterilized according to manufacturer's guidelines, which the NIH Clinical Center sterilization have confirmed they can do as prescribed by the manufacturer in a standard fashion. The remainder of the handheld device is remote from the patient, but can be placed in sterile plastic surgical cover. The Stryker IRF L10 Light Source and Safelight Cable system are part of the Stryker® Infrared Fluorescence (IRF) Imaging System, which is an endoscopic illumination and imaging system for real-time high definition (HD) visible light and near-infrared dye fluorescence imaging of indocyanine green (ICG) during minimally invasive surgery/ procedures. The system complies with IEC 60825-1:2007 and 21 CFR, Subchapter J Parts 1040.10 and 1040.11. This device is designed to ensure electromagnetic compatibility with our electrical medical devices and complies with IEC 6060-1-1-2 requirements for EMC with other devices.

2.3.9 Point-of-care (POC) Optical Molecular Imager (OMI)

This is a camera in a black box taking images of the ex vivo tissue using a BWF1 laser to excite light to see the ICG fluorescence. Specifically, the core biopsy tissue specimen is placed in a sterile container and removed to a windowless room adjacent to the Interventional Radiology (IR) suite. The tissue is placed inside a 2 foot tall black box on a benchtop with the laser. The laser does not come in contact with the patient, nor in the same room as the patient, at any time. (**Figure 15**).

The BWF1 laser generator from the medical laser series will be used with the point of care OMI, which does not occur in vivo, and occurs remote from the patient and not in the procedure room. This system takes pictures of the ex vivo biopsy core itself with special lenses and filters, to display a signal of whether ICG is present in the tissue sample. Although speculative and not part of this study, this assessment might in the future, facilitate examination of future biopsy tissue quality or might point towards the absence or presence of tumor (although no such claims or hypotheses are made in this study).

In the POC epifluorescence OMI system, the fluorescence excitation light is provided by a 450-mW, 785-nm laser (Edmund Optics). Upon the absorption of laser light, the ICG in the vessels is excited and emits infrared light at a different wave length. The camera system captures the infrared emission, processes the image and displays it on a surgical display. Emitted fluorescent light is collected by a close focus video zoom lens (Edmund Optics) and filtered by a band-pass

[figure not shown]

Figure 15. Black Box and contents for sample evaluation.

filter. The filtered fluorescent light is imaged with a near-infrared-optimized high temporal- and high-spatial resolution camera (Mako; Allied Vision Technologies) (**Figure 2**). A new filter slider, which allows for direct visualization of the sample by the POC system, is used for adjusting the sample in the field of view of the camera. A custom-built dark cabinet for the POC eliminates or reduces signal from stray photons in the environment. (**Figure 15** and **Figure 16**).

[figure not shown]

Figure 16. Outside imaging – the black box contents a. stage b. camera c. laser input to excite ICG for imaging.

2.3.10 EM tracking

Aurora (Northern Digital Inc, Waterloo, Ontario, Canada) EM tracking system is used for device tracking. A small electromagnetic field generator is mounted on a modified passive support and positioning arm, and produces an ultra-low electromagnetic field ($<70\mu\text{T}$) enabling simultaneous tracking of the several sensor coils in the inner needle stylet at the beginning of the biopsy, within a work volume of $\sim 500\text{mm}^3$. Commercial and FDA-cleared “PercuNav” needles (Philips) have stylets that contain sensor coils in the needle tips. These needles allow for tracking and mapping location coordinates in relation to the pre-procedural CT or MRI when in the

presence of an EM field generator and a tracking system. During the biopsy (as described above), after both inner and outer biopsy needles are placed in the liver, the coaxial inner stylet is removed and replaced with the OMI scope. The outer needle remains in the liver after the inner stylet is removed, and provides a cannula lumen, through which is placed the scope (for data sampling of fluorescent signal). This occurs once along the way to the target liver lesion - likely in normal liver- and the process is repeated after advancement of the original needle and stylet to the target lesion, during the standard clinically-indicated biopsy (as described above). After optical ICG signal data acquisition, the scope is removed and a standard spring-loaded disposable FDA-cleared biopsy gun takes a tissue specimen from the same location as would have been biopsied in the absence of this study. Thus the FDA-cleared outer cannula introducer allows insertion of the biopsy needles and the pediatric cystoscope-urethroscope via the same outer needle / cannula, using a coaxial approach.

2.3.11 Software

The EM and optical display software components analyze the EM and optical data and signal outside of the body, and the information is not used to guide the needle placement or the biopsy sample. The commercial EM needle, described above, and the commercial EM field generator and its commercial advanced programming interface are analyzed by custom software in order to co-display the local optical signal as well as the EM tracking fusion biopsy location in relation to a pre-procedural CT or MRI image. This information will be analyzed post-procedure, but is not used for navigation of the device. This system and multiple commercial fusion biopsy platforms (UroNav & PercuNav, Philips, for example) have been in clinical use on IRB-approved protocols at NIH for 15 years. These NIH research studies are currently approved under an IDE exemption. The OMI/EM system in its entirety has been thoroughly tested in phantoms as well as live animals (woodchuck liver cancer tumors for biopsy). This *in vivo* testing, included the EM tracking / fusion display components, the OMI pediatric cystoscope-urethroscope, and the combined signal display. This custom software platform incorporates EM fusion co-display (that tracks, fuses, and displays the needle with respect to CT images). The system also combines this EM fusion co-display navigation with the software that adjusts the camera (optical signal) functions from the pediatric cystoscope-urethroscope, and co-displays the OMI camera feed (ICG dye) in real time. DICOM images are loaded onto workstation computer by network transfer directly from the DICOM server/client. The graphical user interface includes tri-planar reconstructed views (sagittal, coronal, and axial) next to the images. The coil sensor in the inner stylet guider needle tip gives position and orientation to reformat and display the corresponding CT display planes. The device location within the registered image is updated in real-time at 10 frames per second. Thus both EM and optical information provide position and ICG levels, respectively, in real time simultaneously. This information however, will NOT be used to guide the biopsy needle to a sample location for biopsy or data sampling. The optical and EM data will be analyzed after the procedure and do not impact the biopsy sampling location.

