6.1.4.3 Post-procedure care

After completion of the procedure, the patients will recover as per standard clinical practice. Participants will be closely monitored for typically 4-6 hours after the procedure as part of their standard post liver biopsy clinical care. All pathological specimens will be evaluated by the NCI Laboratory of Pathology, who will classify the histology of the lesion according to standard criteria. After review, the results of the pathological analysis will be associated with the participant's code.

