9 STATISTICAL CONSIDERATIONS

Three medical procedures will be conducted to diagnose liver lesions as benign/malignant (negative/positive):

- (1) Histopathology, using well-established standard procedures.
- (2) ICG fluorescent signal at the in-vivo site of biopsy using a combination of OMI and EM tracking.
- (3) ICG fluorescent signal ex vivo of the specimen obtained using a combination of OMI and EM tracking.

For (2) and (3), malignancy determination will be based on TBR: $TBR \geq 2$ will produce a malignant diagnosis, and $TBR < 2$ will produce a benign diagnosis.

One main objective is to evaluate the agreement between (1) and (2), and between (1) and (3), with (1) considered as the gold standard. Since determinations are dichotomous, Cohen's kappa will be used to assess agreement.

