9.2 SAMPLE SIZE DETERMINATION

Based on the null kappa value $k_0=0.4$, a kappa value $k_1=0.7$ worth detecting, alpha (Type I error) equal to 0.05, 80% power, and a prevalence (true positive rate) of 80%, the resulting sample size from a one-sided test is 77.

Generally, $\kappa=0.4$ is considered as fair/moderate agreement, and $\kappa=0.7$ as substantial agreement.¹ With an 80% true positive rate, $\kappa=0.4$ corresponds to an 86% sensitivity and 55% specificity, and $\kappa=0.7$ corresponds to a 93% sensitivity and 80% specificity

With data on 77 cases, it is worthwhile determining the optimal cut-off point for TBR to confirm whether $TBR=2$ is optimal. This can be done based on Youden's index in receiver operating characteristic (ROC) analysis.

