9.3.2 Evaluable for objective response

The metric to evaluate where ICG localizes is TBRs and will be calculated by dividing the mean fluorescence intensity within the lesion by the mean fluorescence intensity within the adjacent

¹ Landis, J.R. & Koch, G.G. (1977). "The measurement of observer agreement for categorical data". *Biometrics*, 33 (1): 159–174.

liver parenchyma with in vivo and ex vivo samples. All specimens will be sent to NCI Laboratory of Pathology for diagnosis and research as defined by the patient's primary protocol.

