10.6 CLINICAL MONITORING

The clinical research team will meet on a regular basis when patients are actively receiving an intervention on the trial to discuss each patient.

All data will be collected in a timely manner and reviewed by the principal investigator or a lead associate investigator. Adverse events will be reported as required above. Any safety concerns, new information that might affect either the ethical and or scientific conduct of the trial, or protocol deviations will be immediately reported to the IRB using iRIS.

Accrual and safety data will be monitored by the principal investigator, who will provide oversight to the conduct of this study. The PI will continuously evaluate implementation of the protocol for any unusual or unpredicted complications that occur and will review the data for accuracy and completeness.

The principal investigator will review adverse event and response data on each patient to ensure safety and data accuracy. The principal investigator will personally conduct or supervise the investigation and provide appropriate delegation of responsibilities to other members of the research staff.

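### Nothing requires the TBR value and its malignant/benign call to be fixed before the pathology result is known, so the agreement test is open to review bias

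*Combined protocol and SAP*

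**What the plan says.** **The test.** Section 9 sets histopathology as the reference and TBR as the index test, in vivo and ex vivo: "malignancy determination will be based on TBR: $TBR \geq 2$ will produce a malignant diagnosis", and a lower value is read as benign. Agreement is measured by Cohen's kappa. Section 9.2 plans for "null kappa value $k_0=0.4$, a kappa value $k_1=0.7$ worth detecting", and "the resulting sample size from a one-sided test is 77".

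**How TBR is formed.** Section 9.3.2 obtains it by "dividing the mean fluorescence intensity within the lesion by the mean fluorescence intensity within the adjacent" liver parenchyma. Section 6.1.4.2 has three or more fluorescence measurements attempted.

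**When TBR is formed.** Three sections bear on this and do not agree cleanly:
- Section 2.3.11 places analysis of the optical data after the procedure, without a deadline: "The optical and EM data will be analyzed after the procedure and do not impact the biopsy sampling location". It does not name TBR.
- Section 8.4.1 says the measurements from which TBR is obtained are made in the IR suite.
- Section 9.4.5 lists the TBR measurement under intra-procedural details and histopathology under post-procedural information.

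**When pathology arrives.** Section 6.1.4.2 has the core imaged before it goes to pathology. Section 10.2 expects pathology within 1 ± 2 months of biopsy. Section 6.1.4.3 says that "the results of the pathological analysis will be associated with" the participant's code. Section 9.4.2 lets endpoint analysis proceed per patient while enrolment continues, with the final report by year 5.

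**The concern.** The statistical question is whether TBR agrees with pathology. A reader who knows the pathology can resolve judgement calls towards it without intending to. Those calls include where the lesion region and the background region are drawn, which frame is used, and how measurements are combined. Ex vivo, someone must also decide which part of a core is lesion and which is parenchyma. The cut-off of 2 is fixed, but the ratio put against it is not.

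The sponsor has already recognised that region choice affects the reading. In the phantom work (section 2.3.1) a central region of fixed area was used to limit variability, and triplicate readings were averaged. No corresponding rule appears for patients.

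At stake are the kappa estimate, the sensitivity and specificity that go with it, and the 5% error rate of the one-sided test. Section 2.1 says the correlations might support a larger trial, so an inflated estimate could carry forward.

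**Working it through.** **1. Search for a safeguard.** No section blinds the TBR reader to pathology, sets a time by which TBR is final, fixes regions or frames, says how measurements combine, or states that fluorescence results are withheld from the pathologist. The nearest provisions serve other ends. Coding (2.4.1, 10.3) is for privacy, and withholding study results (9.4.1) concerns participants and care decisions.

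**2. Reproduce the plan's sample size.** Inputs from section 9.2: k0 = 0.4, k1 = 0.7, and "alpha (Type I error) equal to 0.05, 80% power, and a prevalence (true positive rate) of 80" per cent, one-sided. Assume both marginals are 0.80.
- Chance agreement: pe = 0.8² + 0.2² = 0.68.
- Observed agreement at kappa 0.4: po = 0.4 × 0.32 + 0.68 = 0.808.
- Large-sample (Fleiss-Cohen-Everitt) variance terms: Q0 = 1.272 and Q1 = 0.817.
- n = [(1.645 × √1.272 + 0.842 × √0.817) / 0.3]² = 76.03, rounded up to 77. This matches the plan.

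**3. Discordant pairs at the null.** 1 − 0.808 = 0.192, and 0.192 × 77 = 14.8 patients, split evenly between the two discordant cells. The equal-marginal table has sensitivity 88% and specificity 52%. Section 9.2 quotes 86% and 55%, which give kappa 0.394, so the two descriptions are close.

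**4. Effect of one moved call.** Moving one discordant patient into agreement adds (1/77)/0.32 = 0.041 to kappa when moves are shared evenly between the two cells. About 0.2 × 77 = 15.4 benign cases are expected, so one moved benign case shifts specificity by 1/15.4 = 6.5 percentage points. With the planning variance, the test rejects when estimated kappa exceeds 0.4 + 1.645 × √(1.272/77) = 0.611.

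**5. Hypothetical illustration of the test.** At least 100,000 tables of 77 were simulated at true kappa 0.40 (cells 0.704, 0.096, 0.096, 0.104). A fraction of the discordant calls was then moved into agreement. The fractions are assumptions.

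| Discordant calls moved | Patients (mean) | False rejection, planning SE | False rejection, Wald SE |
|---|---|---|---|
| 0% | 0 | 4.0% | 5.9% |
| 10% | about 1.5 | about 10% | 13.7% |
| 20% | about 3 | about 21% | 26.9% |

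The Wald version starts slightly above 5% before any call is moved, so the relevant comparison is down each column.

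**The case against.** **Timing.** The sentence in section 2.3.11 is there to say that the data do not steer the needle, and it does not mention TBR. Sections 8.4.1 and 9.4.5 point to the day of biopsy, and section 2.3.11 itself describes the ICG signal as available in real time. A reader might infer that the plan schedules TBR calculation for after pathology. The documents do not support that. The timing is ambiguous, and the gap is that no section settles it.

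**Who sees what.** Section 10.6 says "The principal investigator will review adverse event and response data on each patient", and a reader might infer that the investigator sees pathology beside TBR for each patient. Section 9.4.1 defines response as localisation of the target lesion or delineation on fluorescence microscopy, so section 10.6 does not show this. Section 9.4.1 also gives review of standard pathology to the primary team. What stands is narrower: section 9.4.5 makes both TBR and histopathology study data, and no order of access is set.

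**Picking among repeats.** A reader might infer that several readings of one site will be available to choose from. One reading in normal liver, one in the lesion and one ex vivo already make three, so the documents do not establish this. The missing combination rule remains.

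**Size.** Only values near 2 can plausibly change side through choice of region. In the small human pilot (section 2.3.5, six patients recruited) target TBRs ran from 2.4 to 13.4 with median 7.9, which gives no sign of clustering at the cut-off. That sample is too small to settle the matter, but the objection to treating the illustration as a forecast is fair.

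**Acquisition.** Images are taken before pathology exists, so acquisition cannot follow the result. The exposure is confined to the later reading steps.

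**Conclusion.** The concern holds as a risk of review bias that the plan leaves open. A TBR finalised with pathology known would breach nothing in the protocol, and such a reading could bias kappa, sensitivity and specificity upward. The documents do not show that this will happen, so it would be wrong to conclude that the type I error is already lost.

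The size is conditional. Under the planning assumptions (kappa 0.40, 80% prevalence, equal marginals, n = 77), about three moved calls would take false rejection from 4-6% to 21-27%. The number of calls moved is hypothetical, and letting every discordant call be movable is generous. The point that survives any choice of fraction is that the test is sensitive to very few patients: each moved call is worth about 0.04 on kappa.

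This should be corrected before more patients are read. A reading made after pathology has been seen cannot be made blind again.

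**What to change.** 1. Reconcile section 2.3.11 with sections 8.4.1 and 9.4.5 so that one statement says when TBR is computed.
2. In sections 6.1.4.2 and 9.4, state that the in vivo and ex vivo TBR are computed by a prespecified rule covering regions, frames and averaging. The final value and the ≥2 / <2 call are then locked with a time stamp before the current biopsy's pathology report is seen by, or linked for, the study team. Locking the value as well as the call also protects the cut-off analysis planned in section 9.2.
3. State that fluorescence results are not given to the pathologist. Section 2.2 already has pathology proceed in the standard way, so this only makes it explicit.
4. Record whether the reader knew of a diagnosis made before biopsy. Sections 2.1 and 8.1 admit patients with diagnosed or confirmed disease, and the lock removes knowledge of the current result only. Full blinding might need a separate reader.

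The cost is protocol wording, a time-stamped database entry, and the discipline of finalising TBR promptly after the biopsy. The images exist before the tissue reaches pathology, so the order is feasible. The sample size stays at 77, with no added procedure for patients.
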